4.2.2 Secondary Study Endpoints

- Change in distress measured by K10 and PANAS across the 3-month follow-up to assess sustained improvement.
- Change in cannabis use measured by TLFB, MCQ-17, DFAQ-CU and CWS across the 3-month follow-up to assess sustained improvement.
- Evaluate the relationship between change in cannabis use metrics and change in distress.

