8.3.2 Electronic Consent & Telehealth medical screening (Visit 1)

- Remote e-consent through SendSafe (*20 minutes*)
- Telehealth medical screen with the study clinician to review medical history and medication history [non-NYU patients may be asked to provide their medical records (e.g. fax to NYU study location)], and determine eligibility based on inclusion/exclusion criteria. (*1 hour*)
- Eligible participants will be scheduled for a baseline visit. A team member who is not involved in the administration of study procedures will randomize and program a tDCS device and study equipment will be shipped to participant.

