8.3.3 Baseline Visit & tDCS Session 1 (Visit 2)

- Train participant to use tDCS device (*20 minutes*)
- Perform tDCS tolerability test (*2 minutes*)
- Perform the Cannabis 1 Panel Drug Test (*5 minutes*)
- Self-report questionnaires and measures (*1 hour*)
- Complete first remotely-supervised tDCS session (*20 minutes*)
[First tDCS session and baseline questionnaires may be divided into two sessions +/- 7 days apart pending participant preference]

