8.3.4 Remotely-Supervised tDCS sessions 2-19 (Visits 3-20)

- 20x20 minutes of active or sham tDCS with simultaneous mindfulness meditation (*20 minutes*)
- Self-report questionnaires will be administered through MyCap at sessions 5, 10, and 15 (*25 minutes*)
- AE reporting

8.3.5 tDCS Session 20 &Treatment-end Visit (Visit 21)

- Participants will complete tDCS session 20 (*20 minutes*)
- Repeat questionnaires and measures completed at baseline (*1 hour*)
- Perform the Cannabis 1 Panel Drug Test (*5 minutes*)
- Equipment return

CONFIDENTIAL

This material is the property of the NYU School of Medicine and Langone Medical Center. Do not disclose or use except as authorized in writing by the study sponsor
Interventional Template Version: 11 January 2019

[Last tDCS session and post-treatment questionnaires may be divided into two sessions +/- 3 days apart pending participant preference]

8.3.6 1, 2, and 3-month follow-up (months 2, 3, and 4, +/- 7 days) (Visits 22-24)

- Repeat questionnaires (30 minutes)
- Repeat cognitive measures and Cannabis 1 Panel Drug Test (only at 3-month follow-up) (35 minutes)
- Unblind after completing 3-month follow-up and brief blinding integrity questionnaire

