10.4.2 Analysis of the Primary and Secondary Endpoint(s)

The efficacy of RS-tDCS to effect the outcomes of each Aim 1 & 2 will be tested using linear mixed effects models. The dependent measures (K10 score, NA, percent of days of use, CWS, MCQ-17) will be nested within timepoint (Visit 1, 5, 10, 15, 20), with active/sham as fixed effects. This will be done using the Matlab function 'fitlme' with REML estimation predicting change from V1 values following each 5 session RS-tDCS interval (Matlab, R2020a, The MathWorks Inc.).

Given that the purpose of this pilot study is to develop effect sizes for a subsequent R01, we will also derive least-squares means effect sizes of our research strategy on distress, NA, percentage of days of use in 4 intervals [V1-V5; V6-V10; V11-V15; V16-V20]. The number of days that elapsed in each interval will be used as a covariate.

CONFIDENTIAL

This material is the property of the NYU School of Medicine and Langone Medical Center. Do not disclose or use except as authorized in writing by the study sponsor
Interventional Template Version: 11 January 2019

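### The efficacy model in section 10.4.2 stops at the end of treatment, so the 1-, 2- and 3-month follow-ups behind two secondary endpoints have no planned active-sham comparison, and its visit labels conflict with section 8.3

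*Combined protocol and SAP*

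**What the plan says.** Section 10.4.2 covers the primary and secondary endpoints together. It plans linear mixed-effects models in which the dependent measures "will be nested within timepoint (Visit 1, 5, 10, 15, 20), with active/sham as fixed effects", with estimation "predicting change from V1 values following each 5 session RS-tDCS interval". It adds least-squares effect sizes for distress, negative affect and "percentage of days of use in 4 intervals [V1-V5; V6-V10; V11-V15; V16-V20". The Protocol Summary repeats the same five visits. Section 10.5 bases the sample size on five timepoints, giving four change scores per measure per participant.

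Section 4.2.1 sets the primary endpoints as change from baseline to treatment-end. Section 4.2.2 sets the secondary ones over a longer span, for example "Change in distress measured by K10 and PANAS across the 3-month follow-up to assess sustained improvement", with a parallel endpoint for cannabis use. Section 3.2 lists persistence of benefit in each domain as a secondary objective.

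Section 8.3 numbers the visits as follows:
- 8.3.2: "Electronic Consent & Telehealth medical screening (Visit 1"
- 8.3.3: "Baseline Visit & tDCS Session 1 (Visit 2"
- 8.3.4: sessions 2 to 19 are Visits 3 to 20, with questionnaires at sessions 5, 10 and 15
- 8.3.5: session 20 is combined with the "Treatment-end Visit (Visit 21"
- 8.3.6: "1, 2, and 3-month follow-up (months 2, 3, and 4, +/- 7 days) (Visits 22-24"

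**The concern.** There are two separate problems.

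The first is a gap. Three follow-up visits are run to measure whether any benefit lasts, yet the section that claims to cover the secondary endpoints lists no timepoint after treatment. The month 1, 2 and 3 data are collected under blinding, since participants are unblinded only after month 3 (sections 8.3.6 and 10.6.3). They could support a randomised comparison, but none is specified. A persistence statement would then depend on an analysis chosen after the data are seen, or on change within the active arm. Within-arm change cannot be credited to stimulation, because both arms receive guided meditation, which sections 2.4.2 and 7.1.1 themselves describe as reducing distress.

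The second is a labelling conflict. Visit 1, 5, 10, 15 and 20 mean one set of assessments if read against section 8.3 and another if read as session numbers. The data go to another institution for analysis (section 10.1). The label V1 also decides what counts as baseline: the K10 is given at phone pre-screening to judge eligibility (section 8.3.1), and the self-report questionnaires are completed at the baseline visit (sections 8.1 and 8.3.3).

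**Working it through.** **Step 1. Visit-to-session mapping.** From section 8.3, session s takes place at Visit s + 1, for s = 1 to 20.

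| Label in 10.4.2 | Read as a section 8.3 visit | Read as a session | Section 8.3 visit for that session |
|---|---|---|---|
| 1 | Consent and screening | Session 1, at the baseline visit | Visit 2 |
| 5 | Session 4 | Session 5 | Visit 6 |
| 10 | Session 9 | Session 10 | Visit 11 |
| 15 | Session 14 | Session 15 | Visit 16 |
| 20 | Session 19 | Session 20, treatment-end | Visit 21 |

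**Step 2. Which reading fits the section itself.** Section 10.4.2 speaks of intervals of five sessions and gives four of them.
- Section 8.3 visit numbers: V1–V5 holds sessions 1–4 (four), V6–V10 holds 5–9, V11–V15 holds 10–14 and V16–V20 holds 15–19. The total is 4 + 5 + 5 + 5 = 19, and session 20 falls in no interval.
- Session numbers: 1–5, 6–10, 11–15 and 16–20. The total is 4 × 5 = 20, with five in each.

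Questionnaires are collected at sessions 5, 10 and 15 and after session 20 (sections 8.1, 8.3.4 and 8.3.5). This matches the session reading at all four post-baseline points and the visit reading at none. Session numbers are therefore the workable reading, and V20 is treatment-end.

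**Step 3. Coverage of the scheduled assessments.** The outcome assessments are baseline, sessions 5, 10 and 15, treatment-end, and months 1, 2 and 3, which makes 8. On the session reading the model uses the first 5. Months 1, 2 and 3 (Visits 22 to 24) are outside it, 3 of 8. On the visit reading they are outside it too, because the list ends at Visit 20.

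**Step 4. Whether another section covers the follow-ups.**
- Section 10.2 states a treatment-by-time interaction hypothesis, allows a regression on continuous time if the plots suggest a trend, and plans covariate models. It names no follow-up visit and no persistence contrast.
- Section 10.4.4 concerns compliance and the change in distress to the end of treatment.
- Section 10.4.6 refers the exploratory outcomes back to the approach used for the primary outcome.
- Section 10.5 counts five timepoints.

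**Step 5. Effect on the sample size.** Section 10.5 uses DE = 1 + (m − 1) × ICC and n = N_effective × DE / m.
- Plan's figure, with m = 5, ICC = 0.8 and N_effective = 50: DE = 1 + 4 × 0.8 = 4.2, and n = 50 × 4.2 / 5 = 42. This reproduces the stated value.
- If all eight assessments were counted, m = 8: DE = 1 + 7 × 0.8 = 6.6, and n = 50 × 6.6 / 8 = 41.25, which rounds up to 42.

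The formula gives 42 either way. If the follow-ups are analysed separately, the basis of m = 5 is not touched at all.

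**The case against.** A reader who takes the visit numbers literally might infer that the model leaves out the treatment-end visit and measures change from screening, so that the primary endpoint is never analysed. The documents do not support this. Section 10.4.2 defines its own timepoints by five-session blocks, the four blocks make up exactly 20 sessions, and the questionnaires fall at sessions 5, 10, 15 and 20. The literal reading would also fail visibly: none of its four post-baseline points has questionnaires, and section 8.3.2 lists none at Visit 1. What remains is a label conflict that should be removed. The table of contents adds to it by listing treatment-end as Visit 22 and the follow-ups as Visits 23 to 25.

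A reader might also infer that section 10.4.2 holds the only efficacy model and that the plan offers nothing but within-arm evidence on persistence. That goes too far. Section 10.2 sets out an active-versus-sham interaction hypothesis and further repeated-measures models without tying them to a visit list, so the intended comparison is plainly between arms. It can fairly be argued that the same approach would carry over to the follow-ups. But section 10.4.2 fixes the timepoints, section 10.5 repeats the count of five, and neither leaves room for months 1 to 3. The follow-up comparison is unspecified, which is a different matter from being ruled out.

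A third objection concerns the remedy, and it stands. Section 10.2 treats the overall interaction as the test of treatment effect. Putting three off-treatment visits into that model would turn the test into a mixture of on-treatment effect and persistence, and would alter the five-timepoint basis of section 10.5. The follow-ups should therefore be analysed separately.

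**Conclusion.** The point holds in two parts of unequal weight.

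The main part does not depend on how Visit is read. Months 1, 2 and 3 are in no specified model, so the two persistence endpoints in section 4.2.2 have no planned active-sham comparison, although section 10.4.2 is headed as covering them. This affects 3 of the 8 scheduled outcome assessments.

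The lesser part is that the V labels in section 10.4.2 and the Protocol Summary contradict the numbering in section 8.3. Taking them as session numbers rests on the five-session wording, the four intervals and the questionnaire schedule, all of which agree. On that reading the primary endpoint is in the model.

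Neither part changes the stated n of 42. The Schedule of Events table is broken in the available text and was not relied on. This should be corrected before analysis, but it does not undermine the design.

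**What to change.** In section 10.4.2 and the Protocol Summary, replace the visit list with named assessments: baseline (Visit 2, before session 1), sessions 5, 10 and 15 (Visits 6, 11 and 16), and session 20/treatment-end (Visit 21). State that change is measured from the Visit 2 baseline. Relabel the intervals V1–V5 to V16–V20 as sessions 1–5, 6–10, 11–15 and 16–20. Bring the visit numbers in the table of contents into line with section 8.3.

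Keep the primary test on these five timepoints. Add a separate secondary mixed model, or a separately specified contrast, that includes months 1, 2 and 3 (Visits 22, 23 and 24). Report the active-minus-sham difference in change from baseline at each follow-up with its confidence interval, for the distress and cannabis-use measures named in section 4.2.2. This would also settle the reference point for change, which section 4.2.2 leaves open.

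The cost is some rewording and a little more analysis. All the assessments are already scheduled and completed before unblinding, and section 10.5 needs no change.

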8.1 Study Procedures

After subjects provide written informed consent, the following research procedures will take place over approximately 4 months:

- A study clinician will conduct a telehealth research screening through Zoom, Webex or phone call to review patients' medical history and confirm eligibility criteria. Ineligible patients may be referred for standard-of-care by the study clinician.
- If eligible, a study team member who is not involved in treatment delivery or assessment will randomize a device. The study equipment, including the tDCS device, headset, saline sponges, single panel cannabis test kit, and laptop computer will be shipped to the participant. The laptop computer will be pre-programmed with the meditation mindfulness programs.
- Baseline & tDCS Session 1:

CONFIDENTIAL

This material is the property of the NYU School of Medicine and Langone Medical Center. Do not disclose or use except as authorized in writing by the study sponsor
Interventional Template Version: 11 January 2019

- Following procedures for our validated protocol^{85-89,91-95}, participants will first receive training on the use of the tDCS device and headset.
- Participants will undergo a 90-second tDCS tolerability test to ensure the stimulation is tolerable. The participant will be given a one-time use code to initiate the stimulation, the tDCS device will ramp up to its target stimulation intensity (2.0mA) and after 90 seconds, participants will be instructed to press “0” to stop the test. Participants are free to stop the test at any time before the 90 seconds. Participants will then be instructed to remove the headset. Participants who cannot tolerate 2.0 mA will be considered a screen failure.
- Participants will be asked to complete a single panel cannabis test by following the instructions included in the test kit. This remote video method of urine strip testing has been used in other studies of participants with substance use disorders in rural communities¹²¹. Following these established protocols, the participant will be instructed to collect a urine sample in the collection cup (off camera) and then in view of the study technician will place a test strip into the cup and show the results. Participants will then be told to follow the disposal procedures included in the kit and wash their hands.

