10.4.4 Adherence and Retention Analyses

Compliance with the interventions will be assessed by summarizing the distributions of numbers and proportions of completed sessions by intervention group. Supportive analyses will evaluate the effects of compliance on results for the primary outcome of change in distress from baseline to end of treatment. Compliance measures will be incorporated into the primary outcome of Aim 1 (distress) analysis models to estimate the effect of compliance on the primary outcome.

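### The effect sizes meant for the R01 are adjusted for days elapsed per interval, a post-randomisation variable, and no unadjusted version is named as the main estimate

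*Combined protocol and SAP*

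**What the plan says.** Section 10.4.2 contains two steps. The first is the efficacy test, a linear mixed model: "The dependent measures (K10 score, NA, percent of days of use, CWS, MCQ-17) will be nested within timepoint (Visit 1, 5, 10, 15, 20"), with arm as the fixed effect. No other covariate is listed.

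The second step produces the numbers for the next grant: "Given that the purpose of this pilot study is to develop effect sizes for a subsequent R01, we will also derive least-squares means effect sizes". These cover distress, negative affect and percentage of days of use over four intervals, V1-V5 to V16-V20. I read V as session number, since the section speaks of five-session intervals. The sentence that follows is: "The number of days that elapsed in each interval will be used as a covariate". No reason is given, and no version of these effect sizes without the covariate is named.

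On timing, section 8.1 says: "If eligible, a study team member who is not involved in treatment delivery or assessment will randomize a device". The equipment is shipped after that, so randomisation precedes session 1. Section 6.1.6 allows roughly four to six weeks for the 20 sessions.

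Attendance appears separately, in section 10.4.4. Compliance is described by arm: "Compliance with the interventions will be assessed by summarizing the distributions of numbers and proportions of completed sessions by intervention group". It is then used for distress only: "Supportive analyses will evaluate the effects of compliance on results for the primary outcome of change in distress from baseline to end of treatment". The model use is: "Compliance measures will be incorporated into the primary outcome of Aim 1 (distress) analysis models to estimate the effect of compliance on the primary outcome".

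**The concern.** A covariate fixed before randomisation leaves the arm contrast as an estimate of the randomised effect. A covariate that arises afterwards need not. Interval length depends on missed and rescheduled sessions, and these could depend on tolerability, mood, cannabis use or the stimulation itself. If arm influences pace, adjustment can remove a part of the effect that works through pace. It can also bring in whatever else makes slow participants differ from fast ones.

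At stake is the quantity that the pilot exists to deliver. A shifted effect size would be carried into the sample size of the next trial, and its confidence interval would not show the shift. Section 10.4.1 otherwise names only baseline characteristics as candidate covariates, so this one departs from the plan's general approach without explanation.

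**Working it through.** **Is the covariate post-randomisation?** Randomisation occurs after the eligibility screen and before shipping (sections 8.1 and 8.3.2). Every interval ends after at least one treatment session. So yes.

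**Does it vary?** Four weeks is 28 days and six weeks is 42 days. Over four intervals that is 28/4 = 7 to 42/4 = 10.5 days each. So yes, within the permitted schedule.

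**Size of the shift.** The plan gives no figure for this point, so the inputs are assumptions. In a linear model without an arm-by-days interaction,

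adjusted contrast − total contrast = −a × ρ (in within-arm outcome SDs),

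where a is the active-minus-sham difference in interval length, in SDs of length, and ρ is the within-arm correlation of length with outcome. With an assumed SD of 2 days, a = (difference in days)/2.

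- Difference 0 days, or ρ = 0: shift 0.
- Difference 0.5 day, ρ = 0.2: 0.25 × 0.2 = 0.05 SD.
- Difference 1 day, ρ = 0.5: 0.5 × 0.5 = 0.25 SD.

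The sign follows −aρ. Lower scores are better here. If active participants are slower and slow participants do worse, the benefit is overstated. If one of those two directions is reversed, it is understated.

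**Check by simulation.** 28 active and 14 sham participants, assumed true effect −0.5 SD, 4,000 runs per row, with a shared unmeasured factor linking length and outcome:

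| a (days at SD 2) | ρ | Mean contrast without days | Mean contrast with days | −aρ |
|---|---|---|---|---|
| 0 (0) | 0.2 | −0.508 | −0.507 | 0 |
| 0 (0) | 0.4 | −0.498 | −0.499 | 0 |
| 0.25 (0.5) | 0 | −0.495 | −0.495 | 0 |
| 0.25 (0.5) | 0.2 | −0.503 | −0.553 | −0.05 |
| 0.25 (0.5) | 0.4 | −0.498 | −0.600 | −0.10 |
| 0.5 (1) | 0 | −0.490 | −0.487 | 0 |
| 0.5 (1) | 0.2 | −0.508 | −0.610 | −0.10 |
| 0.5 (1) | 0.4 | −0.503 | −0.701 | −0.20 |

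The formula holds, and leaving days out recovers the total effect in every row. The 0.25 SD upper end (ρ = 0.5) comes from the formula alone.

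**Yardstick.** Section 10.5 gives a design effect of 1 + 4 × 0.8 = 4.2 and n = 50 × 4.2/5 = 42, which reproduces; the split is 28 and 14. With one-sided alpha 0.05 and 80% power, the detectable difference for one measurement is (1.645 + 0.842) × √(1/28 + 1/14) = 0.81 SD, or 0.81 × √(4.2/5) = 0.75 SD with the plan's factor. A shift of 0.05 SD is 0.05/0.81 = 6% of the first. A shift of 0.25 SD is 0.25/0.75 = 33% of the second.

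**Consequence for the next trial, as an illustration.** Required sample size goes as 1/d². If the true effect is 0.5 SD and the reported one is 0.6, the next trial gets (0.5/0.6)² = 0.69 of the participants it needs. If 0.4 is reported, it gets (0.5/0.4)² = 1.56 times as many.

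**The case against.** The strongest case for the plan has five parts.

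- **Adjustment has a plausible purpose.** Intervals are counted in sessions, so the nominal dose is fixed at five while calendar time varies. Accounting for actual time at assessment is reasonable. This stands as a reason to keep the adjusted version, but not as a reason to make it the only labelled one.
- **The arms may hardly differ in pace.** Sessions are on weekdays and supervised live, the sham mimics sensation, and section 2.2.2 reports completion above 97% in earlier trials. This also stands: the shift may well be near zero. But completing all sessions is not the same as completing them at the same pace, and the window leaves 42 − 28 = 14 days of slack.
- **The mixed model already covers the same outcomes without elapsed days.** True, and it protects the efficacy test. The numbers named for the R01, however, come from the other step.
- **Sampling error is larger.** The standard error of the contrast is √(1/28 + 1/14) = 0.33 SD, above any shift computed here. True, but the interval displays sampling error and does not display this shift.
- **Removal can cost precision.** With no arm difference in pace and ρ = 0.4, the simulated standard deviation of the estimate was 0.327 without days and 0.303 with it. At ρ = 0.2 the two were 0.319 and 0.320.

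A reader might also infer that sessions completed bias the R01 effect sizes. The text does not support that: they enter only supportive distress models whose stated target is the effect of compliance. What remains there is a labelling matter. Completion is not randomised, so its coefficient is an association, and the arm coefficient beside it is not the ITT effect.

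**Conclusion.** The point holds as a risk to the R01 effect sizes, not as a demonstrated bias. The covariate arises after randomisation, so the adjusted contrast equals the total randomised effect only if arm does not affect pace or pace is unrelated to outcome within arm. The documents give no data on either condition. The shift runs from zero to roughly 0.25 SD, of unknown sign, assuming an SD of 2 days, an arm difference of 0 to 1 day and a within-arm correlation of 0 to 0.5.

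Two stronger readings are tempting and should not be drawn. One is that the effect sizes will be biased; nothing in the documents shows that the arms differ in interval length. The other is that the efficacy test is compromised; the days covariate is attached to the effect-size step, and the mixed model lists only timepoint and arm.

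The change is worth making because it protects the pilot's main product at almost no cost.

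**What to change.** In section 10.4.2:

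- Derive the least-squares effect sizes without elapsed days and name these as the main estimate for the R01.
- Keep the version adjusted for elapsed days as a sensitivity analysis, and give the reason for it.
- Report interval length by arm for each of the four intervals, so that a reader can see whether the two versions could differ.
- State the denominator of the percentage of days of use. If it is taken per interval, elapsed days is close to that outcome's own denominator.

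In section 10.4.4, label the compliance models as supportive, non-ITT and associational, and state that they do not supply the R01 effect sizes. An instrumental-variable estimate of a complier effect is optional; no objective asks for one.

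The cost is SAP wording and one small table. No new data are needed. The downside is a small loss of precision in the main estimate if pace predicts outcome but does not differ by arm.
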